##### Preliminary Safety and Efficacy in PD-1 primary Refractory Melanoma

Intratumoral administration of CMP-001 is currently being evaluated in combination with pembrolizumab in subjects with metastatic melanoma resistant to checkpoint inhibitors. In study CMP-001-001, A Multicenter, Open-label Phase 1b clinical Study of CMP-001 in Combination with Pembrolizumab in Subjects with Advanced Melanoma, CMP-001 is being administered intratumorally on a weekly (Schedule A) and Q3W schedule (Schedule B) across a dose range of 1-10 mg. To date, approximately 45 subjects have been treated in the CMP-001-001 study. Preliminary analysis of safety demonstrates an acute toxicity profile that predominantly consists of Grade 1-2 adverse events including mild fever, chills, rigors, nausea, vomiting and occasional hypotension. In some subjects the severity of this adverse event profile is increased. These AEs typically present after the third CMP-001 dose and generally resolve within a few hours with standard supportive care. The mechanism of action associated with the acute toxicity profile appears to resemble symptoms associated with cytokine release. A treatment algorithm has been developed for the management of these reactions and can be found in **Section 5.2.2.7.** CMP-001-001 adverse event summary in Cohort 2 of the Dose Escalation Phase are presented in **Table 4.1.4-1.**

**Table 4.1.4-1: Related AEs Reported in More than One Subject in CMP-001-001 Study**

CMP001-001 Protocol		
Related AEs Reported in More than One Subject*		
	N (%) of Subjects	
	Schedule A^ (N=28)	Schedule B^^ (n=11)
Anemia	4 (14.3%)	-
Chills	15 (53.6%)	-
Constipation	2 (7.1%)	-
Cough	2 (7.1%)	-
Diarrhea	3 (10.7%)	-

Fatigue	7 (25.0%)	2 (18.2%)
Fever	16 (57.1%)	-
Flushing	2 (7.1%)	-
Headache	6 (21.4%)	2 (18.2%)
Hypertension	2 (7.1%)	-
Hypotension	8 (28.6%)	-
Injection Site Pain	2 (7.1%)	3 (27.3%)
Nausea	8 (28.6%)	-
Pruritus	3 (10.7%)	-
Rigors	6 (21.4%)	-
Tachycardia	2 (7.1%)	-
Vomiting	8 (28.6%)	2 (18.2%)

\*Based on EDC data as of 30 May 2017  
 ^ Schedule A includes Cohort 1 (1 mg, n=3); Cohort 2 (3 mg, n=12); Cohort 4 (5 mg, n=6); Cohort 6 (10 mg, n=3); Cohort 8 (10 mg, n=4)  
 ^^ Schedule B includes Cohort 3 (3 mg, n=4); Cohort 5 (5 mg, n=3); Cohort 7 (10 mg, n=3), Cohort 9 (10 mg, n=1)

Preliminary efficacy data, based upon RECIST investigator reads, from the ITT population across both schedules from the 1, 3 and 5 mg cohorts (N=28) demonstrated on ORR of 21.4% (5 PRs, 1 CR). The ORR in subjects treated on Schedule A (N=21) was 24% (5/21; 95% CI 8.2%-47.2%) and on Schedule B (N=7) was 14.3% (1/7; 95 % CI 0.4-57.9%). All responses seen were evidenced at the subject's first follow up scan (12 weeks). Durability or all responses have been seen beyond 24 weeks with some responses being maintained beyond 1 year.

## 4.2 Rationale

### 4.2.1 Rationale for Dose Selection/Regimen/Modification: Nivolumab

Refer to the **eIB** and the nivolumab **SmPC** or **USPI** for preclinical and clinical study data.

Nivolumab at a dose of 3 mg/kg has been approved as monotherapy in melanoma and NSCLC patients. In the current study, nivolumab will be administered at 240 mg Q2W during the Prime Phase. During the Boost Phase, nivolumab will be administered at either 240 mg Q2W or 480mg Q4W depending on physician discretion. The choice of the 240 mg Q2W (or 480mg Q4W) as an appropriate dose for the switch to fixed dosing is based on simulations performed using the population PK model of nivolumab showing that the fixed dose of 240 mg every 2 weeks (and 480mg Q4W) will provide exposures that 1) are optimally consistent with those obtained with the 2 mg/kg dose every 2 weeks, 2) will maintain individual patient exposures in the exposure range established in melanoma as associated with maximal efficacy response and 3) will maintain individual patients exposure in the exposure range established in melanoma that are well tolerated and safe (Freshwater et al. 2017; Long et al. 2018).

A fixed dose regimen will simplify the dosing regimen to be more convenient for physicians and to reduce potential for dosing errors. A fixed dosing scheme will also reduce complexity in the logistical chain at treatment facilities and reduce wastage.

#### **4.2.2 Rationale for Dose Selection/Regimen/Modification: CMP-001**

During the peri-operative period (Prime Phase), CMP-001 5mg will be administered subcutaneously for the first dose (week 1). Thereafter, CMP-001 will be administered intra-tumorally at 10mg weekly (weeks 2-7).

During the post-surgical period (Boost Phase), CMP-001 5mg weekly will be administered subcutaneously every 4 weeks for up to 54 weeks.

Upon initial exposure to CMP-001, antibodies against the Q-beta capsid protein are formed. Thereafter the FC portion of the antibody bind to the FCR- $\gamma$  on the pDC. These antibodies are necessary to facilitate the binding of the VLP to the FC. After the first dose approximately 100% of the subjects exposed to CMP-001 demonstrate the presence of these antibodies. Therefore, to maximize the therapeutic potential of CMP-001 and minimize the number of intratumoral injections, the first dose of CMP-001 will be administered subcutaneously.

The rationale for the weekly schedule is primarily based upon the safety and efficacy results from the ongoing study in metastatic melanoma noted above. A comparison of the weekly and Q3weekly schedule in that study demonstrated a trend towards improved efficacy in the weekly schedule. During the initial safety run-in of this study, a variety of doses were explored based on tumor size. The rationale for the fixed dose during Prime Phase weeks 2-7 is based on the safety and efficacy results from the initial safety run-in that showed no increased incidence of adverse events in patients treated with higher doses of CMP-001.

#### **4.2.3 Rationale for Combining TLR9 Agonist with an Anti PD-1/PD-L1 Antibody**

Toll-like receptors (TLRs) are part of the innate immune system where they recognize and bind conserved pathogen-associated molecular patterns (PAMPs) (Murad and Clay 2009). TLR9 recognizes unmethylated cytosine guanosine dinucleotides (CpG) oligodinucleotides (ODN); and TLR9 agonism activates plasmacytoid dendritic cells (pDC) and B cells, and results in potent T helper-1 (Th-1)-type immune and anti-tumor responses in mouse tumor models and in patients with human cancer (Fourcade et al. 2008). However, while CpG administration strongly induces tumor-specific CD8+ T cell responses, objective responses are rare and T cell responses are not sustained (Fourcade et al. 2008; Appay, Speiser, et al. 2006; Appay, Jandus, et al. 2006). There are 3 classes of CpG ODN: type A which strongly stimulate pDC IFN- $\alpha$  secretion and minimal B cell activation; type B which strongly stimulate B cell proliferation/differentiation and NF- $\kappa$ B activation; and type C which stimulate B cell proliferation/differentiation and moderately stimulate pDC IFN- $\alpha$  secretion (Krieg 2007). Pre-clinically, intra-tumoral CpG synergizes with anti-PD-1 therapy by promoting infiltration of activated TA-specific CD8+ T cells expressing IFN- $\gamma$  and TNF- $\alpha$  (Wang et al. 2016). In patients with advanced melanoma, the combination of type C TLR9 agonist SD-101 and PD-1 inhibitor pembrolizumab is associated with significant responses with minimal additional toxicity (Ribas et al. 2018).

### **5 Methodology**

#### **5.1 Entry Criteria**

##### **5.1.1 Diagnosis/Conditions for Study Entry**

Patients eligible for this study should have locally and/or regionally advanced melanoma that is considered potentially surgically resectable and with biopsy-amenable tumor at baseline.

### 5.1.2 Subject Inclusion Criteria

A patient must meet all of the following criteria to be eligible to participate in this study:

1. Be willing and able to provide written informed consent for the study.
2. Be  $\geq 18$  years of age on day of signing informed consent.
3. Diagnosis of histologically or cytologically confirmed diagnosis of cutaneous melanoma belonging to one of the following AJCC TNM stages:
  - a.  $T_x$  or  $T_{1-4}$  **and**
  - b.  $N_{1b}$ , or  $N_{1c}$ , or  $N_{2b}$ , or  $N_{2c}$ , or  $N_{3b}$ , or  $N_{3c}$  **and**
  - c.  $M_0$

Patients are eligible for this trial either at presentation for primary melanoma with concurrent regional nodal and/or in-transit metastasis; **or** at the time of clinical detected nodal and/or in-transit recurrence; **and may belong to any of the following groups:**

- Primary cutaneous melanoma with clinically apparent regional lymph node metastases.
- Clinically detected recurrent melanoma at the proximal regional lymph node(s) basin.
- Clinically detected primary cutaneous melanoma involving multiple regional nodal groups.
- Clinical detected nodal melanoma (if single site) arising from an unknown primary.
- In-transit and/or satellite metastases with or without regional lymph node involved permitted if considered potentially surgically resectable at baseline.
- **NOTE: Determination of potential resectability must be made at baseline to be eligible for this neoadjuvant study.**
- **NOTE: Patients with mucosal and/or uveal melanoma are not permitted to enroll. Patients with melanomas of unknown primary may be enrolled at the discretion of the treating investigator in discussion with Principal Investigator.**

4. Presence of injectable and measureable disease based on RECIST 1.1.
5. Willing to undergo tumor biopsy (core, punch, incisional or excisional). Patients must undergo biopsy (core, punch) or open biopsy (incisional, excisional) within 4 weeks of registration on the study.
6. Performance status of 0 or 1 on the ECOG Performance Scale.
7. Demonstrate adequate organ function as defined in **Table 5.1.2-1.** performed on screening labs obtained within 4 weeks of registration.

**Table 5.1.2-1: Adequate Organ Function Laboratory Values**

System	Laboratory Value
Hematological	
Absolute neutrophil count (ANC)	$\geq 1,500$ /mcL
Hemoglobin	$\geq 9$ g/dL or $\geq 5.6$ mmol/L
Platelets	$\geq 100,000$ / mcL
Renal	
Serum creatinine OR Measured or calculateda creatinine clearance (GFR can also be used in place of creatinine or	$\leq 1.5$ X upper limit of normal (ULN) OR $\geq 60$ mL/min for subject with creatinine levels $> 1.5$ X institutional ULN

CrCl)	
Hepatic	
Serum total bilirubin	≤ 1.5 X ULN OR Direct bilirubin ≤ ULN for subjects with total bilirubin levels > 1.5 ULN
AST (SGOT) and ALT (SGPT)	≤ 2.5 X ULN
Coagulation	
International Normalized Ratio (INR) or Prothrombin Time (PT)	≤ 1.5 X ULN unless subject is receiving anticoagulant therapy as long as PT or PTT is within therapeutic range of intended use of anticoagulants
Activated Partial Thromboplastin Time (aPTT)	≤ 1.5 X ULN unless subject is receiving anticoagulant therapy as long as PT or PTT is within therapeutic range of intended use of anticoagulants

8. Female subject of childbearing potential should have a negative urine or serum pregnancy within 72 hours prior to receiving the first dose of study medication. If the urine test is positive or cannot be confirmed as negative, a serum pregnancy test will be required.
9. Female subjects of childbearing potential should be willing to use 2 methods of birth control or be surgically sterile, or abstain from heterosexual activity for the course of the study through 26 weeks after the last dose of study medication (**Section 5.7.2**). Subjects of childbearing potential are those who have not been surgically sterilized or have not been free from menses for > 1 year.
10. Male subjects should agree to use an adequate method of contraception starting with the first dose of study therapy through 26 weeks after the last dose of study therapy.

Note: Abstinence is acceptable if this is the usual lifestyle and preferred contraception for the subject.

### 5.1.3 Subject Exclusion Criteria

The subject must be excluded from participating in the trial if the subject:

1. History of uveal or mucosal melanoma.
2. Is currently participating in or has participated in a study of an investigational agent or using an investigational device within 4 weeks of the first dose of treatment.
3. Has a diagnosis of immunodeficiency or is receiving systemic steroid therapy or any other form of immunosuppressive therapy within 7 days prior to the first dose of trial treatment.
4. Has had prior chemotherapy, targeted small molecule therapy, or radiation therapy within 2 weeks prior to study Day 1 or who has not recovered (i.e., ≤ Grade 1 or at baseline) from adverse events due to a previously administered agent.
  - Note: Subjects with ≤ Grade 2 neuropathy are an exception to this criterion and may qualify for the study.
  - Note: If subject received major surgery, they must have recovered adequately from the toxicity and/or complications from the intervention prior to starting therapy.
  - Note: Subjects with autoimmune disorders of Grade 4 while on prior immunotherapy will be excluded. Subjects who developed autoimmune disorders of Grade ≤ 3 may

enroll if the disorder has resolved to Grade ≤1 and the subject has been off systemic steroids at doses >10 mg/d for at least 2 weeks.

5. Active (i.e., symptomatic or growing) central nervous system (CNS) metastases.
6. Has a known additional malignancy that is progressing or requires active treatment. Exceptions include basal cell carcinoma of the skin, squamous cell carcinoma of the skin, or in situ cervical cancer that has undergone potentially curative therapy.
7. Has a systemic disease that requires systemic pharmacologic doses of corticosteroids greater than 10mg daily prednisone (or equivalent). Subjects who are currently receiving steroids at a dose of ≤10mg daily do not need to discontinue steroids prior to enrollment. Subjects that require topical, ophthalmologic and inhalational steroids would not be excluded from the study. Subjects with hypothyroidism stable on hormone replacement or Sjogren's syndrome will not be excluded from the study. Subjects who require active immunosuppression (greater than steroid dose discussed above) for any reason are excluded.
8. Has evidence of interstitial lung disease or active, non-infectious pneumonitis.
9. Has an active infection requiring systemic therapy.
10. Has a history or current evidence of any condition, therapy, or laboratory abnormality that might confound the results of the trial, interfere with the subject's participation for the full duration of the trial, or is not in the best interest of the subject to participate, in the opinion of the treating investigator.
11. Has known psychiatric or substance abuse disorders that would interfere with cooperation with the requirements of the trial.
12. Is pregnant or breastfeeding, or expecting to conceive or father children within the projected duration of the trial, starting with the pre-screening or screening visit through 26 weeks after the last dose of trial treatment.
13. Has received prior therapy with an anti-PD-1, anti-PD-L1, anti-PD-L2, anti-CD137. Prior treatment with ipilimumab or interferon alfa is allowed. Patients with history of allergic or hypersensitivity reaction to interferon alfa or ipilimumab are also excluded.
14. Has a known history of Human Immunodeficiency Virus (HIV) (HIV 1/2 antibodies).
15. Has known active Hepatitis B (e.g., HBsAg reactive) or Hepatitis C (e.g., HCV RNA [qualitative] is detected. Patients with treated Hepatitis B/C with no evidence of active infection may be enrolled.

## **5.2 Trial Treatments**

This is a neoadjuvant biotherapy study testing nivolumab with CMP-001 in patients with locally/regionally advanced/recurrent melanoma. Subjects will receive combination nivolumab/CMP-001 for 7 weeks (Prime Phase) prior to surgery. Surgery will be scheduled approximately 2 – 4 weeks after completion of Prime Phase depending on recovery. After recovery from surgery subjects will receive additional nivolumab/CMP-001 for approximately 46 additional weeks of study drug(s)

administration (Boost Phase). The treatment to be used in this trial is outlined below. Trial treatment should begin within 4 weeks of study registration.

[figure not shown]

Figure 2: Trial Diagram

Allocation of study treatment arm: Up to 40 evaluable patients will be enrolled to receive nivolumab/CMP-001 combination.

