Appendix 1 Dietary History Questionnaire for Microbiome Sampling

Appendix 2 Pathologic Response Assessment (irPRC Criteria)

## 1 Trial Summary

Trial Phase	Non-randomized phase II single arm Simon two-stage
Clinical Indication	PD-1 naïve stage IIIB/C/D melanoma
Trial Type	Neoadjuvant study
Type of control	Not applicable
Route of administration	CMP-001 pre-operatively (intra-tumoral) and post-operatively (subcutaneous) Nivolumab pre- and post- operatively (intravenous)
Trial Blinding	N/A
Treatment Groups	N/A
Number of trial subjects	Total sample size: 33 (1 st stage 14; 2 nd stage 16; 3 additional allowing for dropout)
Estimated enrollment period	15-20 months
Estimated duration of trial	24 months
Duration of Participation	24 months
Estimated average length of treatment per patient	52 weeks

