### **5.8 Subject Replacement Strategy**

Subjects who receive at least 1 dose of CMP-001 and nivolumab are evaluable for safety. Patients who complete pre-operative therapy and receive surgery will be evaluable for pathologic response rate and other efficacy endpoints. Patients who did not undergo surgery for reasons of disease progression precluding surgery (rapid disease progression) will be deemed non-evaluable. Non-evaluable subjects may be replaced.

If in the opinion of the treating investigator and treating surgical oncologist in consultation with Principle Investigator, subject's disease is rapidly progressing to the point that window to intervene surgically is narrowing, treatment may be discontinued to permit surgery. These patients are evaluable for pathological response rate and other efficacy endpoints. These patients are eligible to receive CMP-001/nivolumab during "Boost" phase.

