### 8.3 Sample Size

Several of the agents being utilized in the melanoma armamentarium have been evaluated in the neoadjuvant context including: HDI (Moschos et al. 2006), ipilimumab (Tarihini et al. 2014), pembrolizumab (Forde et al. 2018) and nivolumab/ipilimumab combination (Blank et al. 2018; Amaria et al. 2018). In earlier studies, response was typically assessed using chemotherapy criteria and reported as pathologic complete response (pCR) rates. Cognizant of the different mechanism of action of immuno-oncologic agents, more recent studies have utilized alternative means of assessing response using novel immuno-oncologic agent-specific criteria (major pathologic response or MPR rate) as delineated in **Section 8.4.** In the latter studies, MPR rates reported with PD-1 inhibitors range from 28% (Nivolumab, melanoma) to 45% (Nivolumab/Ipilimumab, melanoma) (Huang et al. 2019; Blank et al. 2018; Amaria et al. 2018).

However, the PD-1/CMP-001 combination has not been evaluated in the neoadjuvant setting and the MPR rate for this combination is unknown. To balance efficacy while minimizing exposure of patients to a potentially ineffective combination, we utilize Simon's minimax two-stage design with MPR as the primary endpoint.

In this study, we will test the null hypothesis of 28% MPR versus the alternative hypothesis of 55% MPR. In the 1st stage, we will enroll 14 evaluable patients (defined in **Section 5.8**). If we see at least 5/14 major pathologic responses, we will enroll a further 16 patients to the 2nd stage. The combination will be considered worthy of further evaluation if ≥13 responses are observed in both stages in 30 evaluable patients. The Simon's **minimax** two-stage design and sample size of 30 evaluable patients provides a type I error rate of 5%, with a power of 0.91. Allowing for 10% drop out rate, we set a total sample size of 33 patients.

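### Section 5.2 permits up to 40 evaluable patients, but Sections 1 and 8.3 plan 30 evaluable from 33 enrolled, and no success rule covers more than 30

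*Combined protocol and SAP*

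**What the plan says.** Three places in the combined protocol and SAP give the size of the trial.

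- **Section 5.2 (Trial Treatments):** "Up to 40 evaluable patients will be enrolled to receive nivolumab/CMP-001 combination".
- **Section 1 (Trial Summary):** "Total sample size: 33", made up of 14 in the first stage, 16 in the second, and "3 additional allowing for dropout".
- **Section 8.3 (Sample Size):** 14 evaluable patients in stage 1, continuing to 16 more if at least 5 respond. The final rule is: "The combination will be considered worthy of further evaluation if ≥13 responses are observed in both stages in 30 evaluable patients". The stated properties are that the "sample size of 30 evaluable patients provides a type I error rate of 5%, with a power of 0.91", and then: "Allowing for 10% drop out rate, we set a total sample size of 33 patients".

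Section 5.8 (Subject Replacement Strategy) adds: "Non-evaluable subjects may be replaced". It does not say that enrolment ends once 30 patients are evaluable, or which patients enter the test if there are more.

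**The concern.** The two sizes cannot both stand. An evaluable maximum of 40 exceeds not only the 30 in the design but also the 33 to be enrolled, and the only design calculation in the document supports 30.

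Two things are at stake. The first is the number of patients exposed: a ceiling of 40 evaluable implies more enrolment than Section 8.3 justifies, although that section gives limiting exposure to a possibly ineffective combination as a reason for the two-stage design. The second is the go/no-go decision. The trial is single-arm and open, so responses are known as they accrue. If more than 30 patients become evaluable, someone has to choose either the 30 to count or a new cut-off, and the plan gives no rule for that choice.

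**Working it through.** **Inputs.** All are from Section 8.3 unless noted.

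- Null and alternative major pathologic response rates: p0 = 0.28, p1 = 0.55.
- Stage 1: n1 = 14, continue if at least 5 respond.
- Final: n = 30, success if at least r = 13 respond.
- Drop-out 10%, total 33.
- Evaluable ceiling 40 (Section 5.2).

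**Formula.** The exact probability of declaring success at response rate p is

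P(success) = Σ over x = 5 to 14 of P(X1 = x) × P(X2 ≥ r − x), with X1 ~ Bin(14, p) and X2 ~ Bin(n − 14, p).

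Setting p = p0 gives the type I error (alpha) and p = p1 gives the power.

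**Step 1: the plan's own figures.** With n = 30 and r = 13, alpha = 0.0470 and power = 0.907. These agree with the stated 5% and 0.91, so the design in Section 8.3 reproduces. The total also reproduces by the plan's method: 30 × 1.1 = 33.

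**Step 2: can the 40 be derived from the 30 or the 33?** Forty evaluable would need 40 × 1.1 = 44 enrolled by the plan's method, or 40 / 0.9 = 44.4, so 45, by dividing by the retention rate. That is 11 to 12 more than 33. Replacing non-evaluable subjects restores the evaluable count to 30 but does not raise the target to 40.

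**Step 3: the cut-off of 13 carried to other sizes, stage 1 rule unchanged.**

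| Evaluable n | Alpha | Power |
|---|---|---|
| 28 | 0.0274 | 0.852 |
| 29 | 0.0364 | 0.884 |
| **30 (as planned)** | **0.0470** | **0.907** |
| 31 | 0.0591 | 0.924 |
| 32 | 0.0725 | 0.935 |
| 33 | 0.0871 | 0.943 |
| 40 | 0.2005 | 0.957 |

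Alpha passes 5% from the 31st evaluable patient. Below 30, alpha stays under 5% and power falls.

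**Step 4: smallest cut-off that keeps alpha at or below 5%.**

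| Evaluable n | Cut-off | Alpha | Power |
|---|---|---|---|
| 31 | 14 | 0.0286 | 0.882 |
| 32 | 14 | 0.0371 | 0.905 |
| 33 | 14 | 0.0470 | 0.922 |
| 34 | 15 | 0.0293 | 0.903 |
| 35 | 15 | 0.0374 | 0.920 |
| 36 | 15 | 0.0467 | 0.932 |
| 37 | 16 | 0.0298 | 0.918 |
| 38 | 16 | 0.0374 | 0.930 |
| 39 | 16 | 0.0462 | 0.939 |
| 40 | 17 | 0.0300 | 0.929 |

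At n = 40, a cut-off of 16 is not enough: alpha is 0.0560.

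**Step 5: how much of this arises without the 40.** Assume 33 are enrolled and drop-outs D ~ Bin(33, 0.1).

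- More than 30 evaluable means D ≤ 2, which has probability 0.346 (0.031 for 33 evaluable, 0.113 for 32, 0.201 for 31).
- If shortfalls are replaced up to 30, the evaluable number is max(30, 33 − D). Always applying 13 gives 0.031 × 0.0871 + 0.113 × 0.0725 + 0.201 × 0.0591 + 0.654 × 0.0470 = 0.0536 (from unrounded probabilities).
- If shortfalls are not replaced, the evaluable number is 33 − D, and the same averaging gives 0.046.

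**The case against.** The strongest reply is that the statistical section is complete and correct. It fixes 14 evaluable patients, then 16 more, then a cut-off for 30, and its error rates reproduce. Section 1 agrees with it. The odd one out is a single sentence in a treatment section, and since it sets a ceiling, a trial that stops at 30 evaluable does not breach it. A natural reading of the stage counts is that stage 2 closes at 30, and Section 5.8 allows replacement only of non-evaluable subjects. The inflated error rates come from applying 13 to a set other than the one the rule names, which no section tells anyone to do. Nor does any section plan for 44 or 45 enrolled. Without the 40, whether overall alpha exceeds 5% depends on replacement: 5.4% with it, 4.6% without.

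Much of this stands. The 13-of-30 test is valid as written, the 20.1% is conditional on misapplying the cut-off, and the effect without the 40 is small. It does not remove the contradiction. A ceiling of 40 evaluable is still above the total of 33 to be enrolled, and both statements are current text. Stopping at 30 evaluable is an inference that the document never states, and at full enrolment of 33 with the plan's own drop-out rate there is about a one-in-three chance (34.6%) of more than 30 evaluable.

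**Conclusion.** The concern holds. Section 5.2 is inconsistent with Sections 1 and 8.3 on the size of the trial, and neither drop-out, replacement nor reading the 40 as a ceiling reconciles them. This must be corrected because the enrolment limit and the primary decision rule both depend on that number.

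The stated test itself is not in error: 13 of 30 gives alpha 4.7% and power 90.7%. The error rate is at risk only if the cut-off of 13 is used with more than 30 patients. In that case alpha is 5.9% at 31, 8.7% at 33 and 20.1% at 40, assuming the stage 1 rule of 5 of 14 is unchanged. With 33 enrolled and the 40 set aside, overall alpha is 5.4% under 10% independent drop-out with replacement up to 30, so the serious exposure comes from the figure in Section 5.2.

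**What to change.** 1. Correct the sentence in Section 5.2 to 30 evaluable patients and 33 enrolled, as in Sections 1 and 8.3, unless the sponsor confirms that another size is intended.
2. Add to Section 8.3: *The primary decision uses the first 30 evaluable patients in order of enrolment (the first 14, then the next 16). Any further evaluable patients are reported only in the MPR estimate and its exact 95% confidence interval.* Other conventions would also work, provided one is fixed in advance.
3. If the sponsor does intend to test a larger number, restate the cut-off beforehand. Examples are at least 14 of 33 (alpha 4.7%, power 92.2%) or at least 17 of 40 (alpha 3.0%, power 92.9%). The second table above covers every size from 31 to 40.

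The first two changes cost one corrected sentence and two added ones, with no added patients. The downside is that, with 33 enrolled, up to three evaluable patients may not count toward the go/no-go decision, although they still contribute to the estimate.
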